7. REGULATORY ISSUES

7.1. ETHICS APPROVAL

The Study Coordination Centre has obtained approval from the North West London Research Ethics Committee (REC) and Health Regulator Authority (HRA). The study must also receive confirmation of capacity and capability from each participating NHS Trust before accepting

participants into the study or any research activity is carried out. The study will be conducted in accordance with the recommendations for physicians involved in research on human subjects adopted by the 18th World Medical Assembly, Helsinki 1964 and later revisions.

7.2. CONSENT

Consent to enter the study must be sought from each participant only after a full explanation has been given, an information leaflet offered and time allowed for consideration. Signed participant consent should be obtained. The right of the participant to refuse to participate without giving reasons must be respected. After the participant has entered the study the clinician remains free to give alternative treatment to that specified in the protocol at any stage if he/she feels it is in the participant's best interest, but the reasons for doing so should be recorded. In these cases the participants remain within the study for the purposes of follow-up and data analysis. All participants are free to withdraw at any time from the protocol treatment without giving reasons and without prejudicing further treatment.

7.3. CONFIDENTIALITY

The Chief Investigator will preserve the confidentiality of participants taking part in the study and is registered under the Data Protection Act.

Data will be pseudonymised.

7.4. INDEMNITY

Imperial College Healthcare NHS Trust holds standard NHS Hospital Indemnity and insurance cover with NHS Resolution for NHS Trusts in England, which apply to this study.

7.5. SPONSOR

Imperial College Healthcare NHS Trust will act as the main Sponsor for this study. Delegated responsibilities will be assigned to the NHS trusts taking part in this study.

7.6. FUNDING

Imperial Health Charity are funding this study (via the Innovate Grant)

7.7. AUDITS

The study may be subject to audit by Imperial College London/ Imperial College Healthcare NHS Trust under their remit as sponsor and other regulatory bodies to ensure adherence to GCP and the UK Policy Frame Work for Health and Social Care Research.

8. STUDY MANAGEMENT

The day-to-day management of the study will be co-ordinated through a Trial Management Group. This will be chaired by the Chief Investigator and will include all members of the named research team

9. PUBLICATION POLICY

Results will be published in a peer-reviewed journal and presented at relevant national and international conferences.

11. APPENDICES

11.1. CLIENT SATISFACTION QUESTIONNAIRE (CSQ-8)

The Client Satisfaction Questionnaire (CSQ) instruments are self-report questionnaires constructed to measure satisfaction with services received by individuals²⁹.

The CSQ-8 is an 8-item questionnaire that measures the most salient items for the measurement of satisfaction with services:

Questionnaire Item	Scoring			
	4	3	2	1
How would you rate the quality of the service you received?	Excellent	Good	Fair	Poor
Did you get the kind of service you wanted?	Yes definitely	Yes generally	No not at all	No definitely not
To what extent has our service met your needs?	Almost all met	Most met	Only a few met	None met
If a friend were in need of similar help would you recommend our service?	Yes definitely	Yes I think so	No I do not think so	Definitely not
How satisfied are you with the amount of help you received?	Very satisfied	Mostly satisfied	Indifferent	Quite dissatisfied
Have the services you received helped you to deal more effectively with your problems?	Yes a great deal	Yes somewhat	No did not help	No made it worse
In an overall sense, how satisfied are you with the service you have received?	Very satisfied	Mostly satisfied	Indifferent	Quite dissatisfied
If you were seeking help again, would you come back to our service?	Yes definitely	Yes I think so	No I do not think so	No definitely not

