6. STATISTICS AND DATA ANALYSIS

Two hundred and six patients in total will be randomised using an online randomisation tool. <https://www.graphpad.com/quickcalcs/randomize1.cfm>

Patient satisfaction, the primary endpoint measured by CSQ-8, is expected to be approximately 30 in both arms. VAC and SVC will be considered equivalent if the VAC satisfaction score is no more than 1.5 points lower than the SVC score. With 103 subjects in the Control Group (SVC) and 103 subjects in Experimental Group (VAC), there is an 85% chance that the observed difference (SVC-VAC) in satisfaction scores will be significantly less than 1.5 at the 5% level, if the true means are 30 in both groups. The standard deviation has been assumed to be 4.

After the first 50 participants have been entered into the trial a feasibility analysis will be undertaken. Three outcomes of particular interest will be the accrual rate, the proportion accepting their randomisation and the proportion evaluable (completing all questionnaires). With 50 participants it will be possible to estimate the proportions in the latter two groups with 95% confidence intervals of at most $\pm 15\%$. A record will be kept of the number of participants approached and their reasons for declining to enter the study. With 50 participants it should be possible to identify and remedy any minor issues that are impediments to recruitment. It may be necessary to plan to increase accrual if withdrawals or the number of non-evaluable participants is greater than expected.

The primary analysis will be by intention to treat (ITT). It is planned to make comparisons between groups for normally distributed variables with independent samples t-test or ANOVA, variables that are not normally distributed will be analysed with Mann–Whitney U-tests. The Chi-squared or Fisher's exact test will be used to compare proportions and Pearson Product or Spearman Rank statistics will be used to assess correlation. Multiple regression exploratory analyses may be employed to estimate multiple effects simultaneously.

Data and all appropriate documentation will be stored for a minimum of 5 years after the completion of the study, including the follow-up period.

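### Item 2 of the primary-outcome questionnaire, as printed, has two lower response options with no clear order, so the choice between 1 and 2 points is close to arbitrary; the effect is small and the check costs almost nothing.

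*Combined protocol and SAP*

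**What the plan says.** Section 3.5 of the combined protocol and SAP names the CSQ-8 as the measure of the primary outcome and points to appendix 11.1 for the form. That appendix prints eight items, each scored 4, 3, 2 or 1, so the total runs from 8 to 32. Three sets of labels matter here:

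- **Item 2**, "Did you get the kind of service you wanted": *Yes definitely* (4), *Yes generally* (3), *No not at all* (2), *No definitely not* (1).
- **Items 4 and 8**: the score-2 option is a hesitant no and the score-1 option is a definite no.
- **Items 5 and 7** (item 5 is "How satisfied are you with the amount of help you received"): *Very satisfied* (4), *Mostly satisfied* (3), *Indifferent* (2), *Quite dissatisfied* (1).

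Section 6 sets the decision rule: "VAC and SVC will be considered equivalent if the VAC satisfaction score is no more than 1.5 points lower than the SVC score". It also gives the planning value: "Patient satisfaction, the primary endpoint measured by CSQ-8, is expected to be approximately 30 in both arms". The assumed SD is 4, with 103 participants per arm. Section 5 plans a single completion straight after the consent process and no later follow-up.

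**The concern.** A summed score assumes that a lower number on an item means less satisfaction. On item 2 the step from 2 to 1 does not clearly carry that meaning. Both labels are flat refusals, and nothing on the page tells a participant which is the milder. The graded pairs in items 4 and 8 show what an ordered lower half looks like in the same table. The rest of the table reads coherently, so a fault of text extraction is unlikely.

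The item belongs to the sole primary endpoint and is answered once, so an arbitrary answer is not corrected by a later measurement. The direction matters too. The rule accepts video-assisted consent unless it is shown to be worse by the margin, so blurring the low scores can pull a real deficit towards zero. Having the same labels in both arms does not make that harmless under such a rule.

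**Working it through.** **Inputs.** From section 6: mean 30 in both arms, SD 4, margin 1.5, 103 per arm, 5% level, power 85%. From appendix 11.1: eight items scored 1 to 4. Two assumptions are not in the documents: lost points (32 minus the mean) are spread evenly over the eight items, and both arms lose points on item 2 in the same way.

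**1. The plan's own figure.** SE = 4 × √(2/103) = 0.557. Power = Φ(1.5/0.557 − 1.645) = Φ(2.691 − 1.645) = 85.2%. This reproduces the stated 85% as a one-sided 5% test of means with a true difference of zero. The plan does not state sidedness. A one-sided 2.5% test would give 76.8%, so the one-sided 5% reading is used below.

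**2. Where the margin sits on the item scale.** A mean of 30 is 30/8 = 3.75 per item. A mean at the margin, 28.5, is 28.5/8 = 3.56 per item. A drop of that size can come wholly from answers moving from 4 to 3, and those two options are clearly ordered on every item.

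**3. Are low answers to be expected at all?** Yes. Mean 30 and SD 4 under a ceiling of 32 force a lower tail. For example, 80% scoring 32 and 20% scoring 22 gives mean 0.8 × 32 + 0.2 × 22 = 30 and variance 0.8 × 2² + 0.2 × 8² = 16. A total of 22 needs at least one answer of 1 or 2, though not necessarily on item 2.

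**4. If the choice between 1 and 2 is random.** At mean 30 the loss per item is (32 − 30)/8 = 0.25 points. An answer of 2 or lower loses at least 2 points, so at most 0.25/2 = 12.5% of item 2 answers can be that low. A random choice between 1 and 2 has variance 0.25, so the added variance is at most 0.125 × 0.25 = 0.031. The SD becomes √16.031 = 4.004 and power stays at 85.2%.

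**5. If 1 and 2 cannot be told apart and every such answer is recorded as 2.** Take the extreme in which all points lost on item 2 come from answers that should score 1, each losing 3 points.

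| | Mean 30 | Mean 28.5 |
|---|---|---|
| Points lost per item | 0.25 | 0.4375 |
| Share that should score 1 (loss/3) | 0.0833 | 0.1458 |

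Each such answer is recorded one point too high, so the difference between arms shrinks by 0.1458 − 0.0833 = 0.0625. A true deficit of 1.5 is measured as 1.4375, about 1.44. The one-sided error at the margin is Φ(0.0625/0.557 − 1.645) = Φ(−1.533) = 6.3%, against a nominal 5%.

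**6. Sensitivity to the two assumptions.** If item 2 carried twice its even share of lost points, the shrinkage would be 2 × 0.0625 = 0.125, the measured deficit 1.375, and the error Φ(0.125/0.557 − 1.645) = 7.8%. If only the video arm's item 2 losses came from answers that should score 1, the shrinkage would be 0.1458, the measured deficit 1.354, and the error Φ(0.1458/0.557 − 1.645) = 8.3%. With no answers that should score 1 in either arm, the shrinkage is zero and the error stays at 5%.

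**7. Ceiling on the effect.** The ambiguity can move one participant's total by at most 1 point, so item 2 alone can never shift the difference between arm means by 1.5.

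**The case against.** The strongest reply is that the numerical effect is slight and the labels are the same in both arms. Section 6 compares mean totals near the top of the scale and sets no low-score threshold. A failure could show entirely in the well-ordered 4-to-3 step. All of that stands, and it is why this is an instrument check and not a challenge to the design. It does not remove the fault in item 2, which is visible on the page of the primary-outcome form.

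A reader might infer more than the documents support, in three ways:

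- **That items 5 and 7 are faulty as well.** Their options run in the correct order. They lack a mildly dissatisfied option, but any four-point item leaves gaps. Treating all three items as unable to separate 1 from 2 would give a measured deficit of 1.31 and an error of about 9.5%, but *Indifferent* and *Quite dissatisfied* are plainly distinct, so that case does not apply.
- **That the primary score is unreliable where the 1.5-point rule operates.** The second step of the working shows that the rule does not depend on separating 1 from 2.
- **That the share of totals below 24 bounds the effect.** Mean 30 and SD 4 put that share between 1.04% and 21.3%, but a total below 24 does not require a low answer on item 2. Conversely, seven 4s and a 2 on item 2 total 30. The share is therefore neither a floor nor a ceiling for use of item 2's lower options.

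It is also fair to say that the documents do not reproduce the source instrument. Whether any printed label departs from it cannot be shown here.

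**Conclusion.** The point holds for one item of eight. As printed, item 2's score-2 and score-1 labels have no clear order, so which of the two scores a dissatisfied participant receives is close to arbitrary. The documents do not establish that the order is reversed, only that it is unclear.

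The sample size and power are unaffected. With lost points spread evenly over the items and the same pattern in both arms, the extreme case is a 1.5-point deficit read as about 1.44 and an error at the margin of about 6% in place of 5%, in the direction that favours accepting video-assisted consent. Those figures depend on the two assumptions and are not absolute bounds; the departures tried reach about 8%. All of these cases suppose that scores 1 and 2 are wholly indistinguishable, so the likely effect is smaller. This is a minor but real fault in the primary instrument, worth correcting because correction is nearly free.

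**What to change.** Before the form is used, check every response option in the appendix 11.1 table against the source instrument cited as reference 29, and correct any mismatch. In particular, replace item 2's score-2 label so that it is a milder no than the score-1 label. Keep the 8 to 32 scoring. Leave items 5 and 7 as they are unless the check shows a mismatch, because rewording them without cause could break comparability with the cited scale. Carry the corrected wording into the form participants complete, in whatever medium; section 3.5.2 does not say whether the CSQ-8 is completed online.

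The cost is a read-through of one table and a wording change to one row, or to more if the check finds other mismatches. It needs no extra participants, visits or analyses.

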11.2. HEALTH LITERACY ASSESSMENT

Health literacy is defined as ‘the cognitive and social skills that determine the motivation and ability of individuals to gain access to, understand and use information in ways that promote and maintain good health’²⁸.

Health literacy may be an important confounding factor within this study. The Newest Vital Sign (NVS)-UK is a simple, accurate and validated predictor of health literacy skills that has been shown to take on average 3 minutes to complete, and can be administered by both clinical and non-clinical personnel³⁰.

NVS consists of a food nutrition label with six associated questions giving scores from 0 to 6

Product Description: Ice Cream	
Serving Size:	100ml
Servings per container:	4
NUTRITIONAL INFORMATION	
TYPICAL VALUES	Per 100ml
Energy	1050 kJ 250 kcal (calories)
Protein	4 g
Carbohydrate	30 g
of which sugars	23 g
Fat	13 g
of which saturates	9 g
of which monounsaturates	0 g
of which polyunsaturates	3 g
of which trans fats	1 g
Fibre	0 g
Sodium	0.05 g
Ingredients: Cream, Skimmed Milk, Sugar, Whole Egg, Stabilisers (Guar Gum), Peanut Oil, Vanilla Extract (0.05%).	

Question	Correct response
1. How many calories (kcal) will you eat if you eat the whole container?	1,000 KCAL or 1,000 CALORIES
2. If you are advised to eat no more than 60 grams of carbohydrate for dessert, what is the maximum amount of ice cream you could have?	Two servings (or anything up to 2 servings) OR Half the container (or any amount up to half the container) OR 200 ml (or any amount up to 200 ml).
3. Imagine that your doctor advises you to reduce the amount of saturated fat in your diet. You usually have 42 g of saturated fat each day, some of which comes from one serving of ice cream. If you stop eating ice cream, how many grams of saturated fat would you be eating each day?	33 g
4. If you usually eat 2500 calories each day, what percentage of your daily calorie (kcal) intake will you get if you eat one serving of ice cream?	1/10 (one tenth) OR 10%
Imagine that you are allergic to the following substances: penicillin, peanuts, latex gloves, and bee stings.	
5. Is it safe for you to eat this ice cream?	No
If 'No' to Q5:	
6. Why not?	Because it contains peanut oil/peanuts/nuts OR Because you might have an allergic reaction
ASK IF answer to Q6 is 'Because you might have an allergic reaction':	
7. Why would you have an allergic reaction?	Because it contains peanut oil/peanuts/nuts

11.3. KNOWLEDGE AND PERCEPTION QUESTIONNAIRE

SECTION1: PREVIOUS EXPERIENCE

1. Have you been anaesthetised before? Yes ___ No ___
 - 1.1 If so, what type (or types) of anaesthesia?

General anaesthesia ____
 Spinal or epidural (lower half of the body) ____
 Nerve block (for example only arm, hand or foot anaesthesia) ____
 Local anaesthesia ____

2. If you have been anaesthetised, have you experienced any complication related to anaesthesia?
 Yes ____ What?

No ____
 I have never been anaesthetised ____

3. Do you know anyone who has experienced complications related to regional anaesthesia?
 Yes ____ What?

No ____

SECTION 2: KNOWLEDGE OF ANAESTHESIA

4. How many options do you have for your anaesthetic for your operation?
 0 ____ 1 ____ 2 ____ More than 2 ____ Don't Know ____

5. Having which type of anaesthetic will mean that you are awake for your surgery?
 General ____ Regional ____ Both ____ Don't Know ____

6. Which type of anaesthetic is associated with the following statements:
- | | |
|--------------------------------------|--|
| A cannula is inserted into your hand | General ____ Regional ____ Both ____ Don't Know ____ |
| Monitors are applied to your body | General ____ Regional ____ Both ____ Don't Know ____ |
| A tube is inserted into your throat | General ____ Regional ____ Both ____ Don't Know ____ |
| You can listen to your own music | General ____ Regional ____ Both ____ Don't Know ____ |
| You will have a heavy, numb arm | General ____ Regional ____ Both ____ Don't Know ____ |

7. When having **general anaesthesia**, how common is it to experience each one of the following events?

How common is it to:	Very rare	Rare	Uncommon	Common	Very Common
Experience nausea or vomiting	1	2	3	4	5
Have a sore throat	1	2	3	4	5

Suffer confusion, disorientation or memory loss	1	2	3	4	5
Experience pain whilst having the anaesthetic	1	2	3	4	5
Feel anything during surgery	1	2	3	4	5
Have damage caused to your teeth	1	2	3	4	5
Have permanent nerve damage	1	2	3	4	5
Suffer a life-threatening event	1	2	3	4	5
Be aware of your surroundings during surgery	1	2	3	4	5

8. When having **regional anaesthesia (nerve block)**, how common is it to experience each one of the following events?

How common is it to:	Very rare	Rare	Uncommon	Common	Very Common
Experience nausea or vomiting	1	2	3	4	5
Have a sore throat	1	2	3	4	5
Suffer confusion, disorientation or memory loss	1	2	3	4	5
Experience pain whilst having the anaesthetic	1	2	3	4	5
Feel anything during surgery	1	2	3	4	5
Have damage caused to your teeth	1	2	3	4	5
Have permanent nerve damage	1	2	3	4	5
Suffer a life-threatening event	1	2	3	4	5
Be aware of your surroundings during surgery	1	2	3	4	5

9. For the following statements, choose **general anaesthesia** or **regional anaesthesia** as the best option:

It is easier to manage postoperative pain. General ___ Regional ___ Don't Know ___

You will need less painkillers after your operation. General ___ Regional ___ Don't Know ___

You will be able to eat and drink straight away. General ___ Regional ___ Don't Know ___

You will be able to go home more quickly. General ___ Regional ___ Don't Know ___

You will feel like your normal self more quickly. General ___ Regional ___ Don't Know ___

SECTION 3: ATTITUDES TO ANAESTHESIA

10. How anxious do you feel about having an anaesthetic?

Very calm ___ Calm ___ Slightly anxious ___ Anxious ___ Very anxious ___

11. Do you consider **general anaesthesia** as a:
Very safe procedure ___ Safe procedure ___ Risky procedure ___ Very risky procedure ___

12. Do you consider **regional anaesthesia (nerve block)** as a:
Very safe procedure ___ Safe procedure ___ Risky procedure ___ Very risky procedure ___

13. How do you feel about the possibility of being awake during the surgery?
Very calm ___ Calm ___ Slightly anxious ___ Anxious ___ Very anxious ___

14. Imagine that you are having a **general anaesthetic**. How afraid are you about each of the following events?

How afraid are you of:	Very unafraid	Unafraid	Neither afraid or unafraid	Afraid	Very Afraid
Experiencing nausea or vomiting	1	2	3	4	5
Having a sore throat	1	2	3	4	5
Suffering confusion, disorientation or memory loss	1	2	3	4	5
Experiencing pain whilst having the anaesthetic	1	2	3	4	5
Feeling anything during surgery	1	2	3	4	5
Having damage caused to your teeth	1	2	3	4	5
Having permanent nerve damage	1	2	3	4	5
Suffering a life-threatening event	1	2	3	4	5
Being aware of your surroundings during surgery	1	2	3	4	5

15. Imagine that you are having **regional anaesthesia**. How afraid are you about each of the following events?

How afraid are you of:	Very unafraid	Unafraid	Neither afraid or unafraid	Afraid	Very Afraid
Experiencing nausea or vomiting	1	2	3	4	5
Having a sore throat	1	2	3	4	5
Suffering confusion, disorientation or memory loss	1	2	3	4	5
Experiencing pain whilst having the anaesthetic	1	2	3	4	5
Being in pain or feeling anything during surgery	1	2	3	4	5
Having damage caused to your teeth	1	2	3	4	5
Having permanent nerve damage	1	2	3	4	5

Suffering a life-threatening event	1	2	3	4	5
Being aware of your surroundings during surgery	1	2	3	4	5

SECTION 4: PRACTICES TOWARDS ANAESTHESIA

16. Which option for anaesthesia would you choose for your surgery?

General anaesthesia ____ Regional anaesthesia ____

16.1 Why?

17 If your anaesthetist advised you to have a regional anaesthetic technique, would you accept it?

Yes ____ No ____
